## 8.3 ADVERSE EVENTS AND SERIOUS ADVERSE EVENTS

### 8.3.1 DEFINITION OF ADVERSE EVENTS (AE)

Adverse event means any untoward medical occurrence associated with the use of an intervention in humans, whether or not considered intervention-related (21 CFR 312.32 (a)).

### 8.3.2 DEFINITION OF SERIOUS ADVERSE EVENTS (SAE)

An adverse event (AE) or suspected adverse reaction is considered "serious" if, in the view of either the investigator or sponsor, it results in any of the following outcomes: death, a life-threatening adverse event, inpatient hospitalization or prolongation of existing hospitalization, a persistent or significant incapacity or substantial disruption of the ability to conduct normal life functions, or a congenital anomaly/birth defect. Important medical events that may not result in death, be life-threatening, or require hospitalization may be considered serious when, based upon appropriate medical judgment, they may jeopardize the participant and may require medical or surgical intervention to prevent one of the outcomes listed in this definition.

### 8.3.3 CLASSIFICATION OF AN ADVERSE EVENT

#### 8.3.3.1 SEVERITY OF EVENT

- **Mild** – Events require minimal or no treatment and do not interfere with the participant's daily activities.
- **Moderate** – Events result in a low level of inconvenience or concern with the therapeutic measures. Moderate events may cause some interference with functioning.
- **Severe** – Events interrupt a participant's usual daily activity and may require systemic drug therapy or other treatment. Severe events are usually potentially life-threatening or incapacitating. Of note, the term "severe" does not necessarily equate to "serious".]

#### 8.3.3.2 RELATIONSHIP TO STUDY INTERVENTION

All adverse events (AEs) must have their relationship to study intervention assessed by the clinician who examines and evaluates the participant based on temporal relationship and his/her clinical judgment. The degree of certainty about causality will be graded using the categories below. In a clinical trial, the study product must always be suspect.

- **Related** – The AE is known to occur with the study intervention, there is a reasonable possibility that the study intervention caused the AE, or there is a temporal relationship between the study intervention and event. Reasonable possibility means that there is evidence to suggest a causal relationship between the study intervention and the AE.
- **Not Related** – There is not a reasonable possibility that the administration of the study intervention caused the event, there is no temporal relationship between the study intervention and event onset, or an alternate etiology has been established.

OR

- **Definitely Related** – There is clear evidence to suggest a causal relationship, and other possible contributing factors can be ruled out. The clinical event, including an abnormal laboratory test result, occurs in a plausible time relationship to study intervention administration and cannot be explained by concurrent disease or other drugs or chemicals. The response to withdrawal of the study intervention (dechallenge) should be clinically plausible. The event must be pharmacologically or phenomenologically definitive, with use of a satisfactory rechallenge procedure if necessary.
- **Probably Related** – There is evidence to suggest a causal relationship, and the influence of other factors is unlikely. The clinical event, including an abnormal laboratory test result, occurs within a reasonable time after administration of the study intervention, is unlikely to be attributed to concurrent disease or other drugs or chemicals, and follows a clinically reasonable response on withdrawal (dechallenge). Rechallenge information is not required to fulfill this definition.
- **Potentially Related** – There is some evidence to suggest a causal relationship (e.g., the event occurred within a reasonable time after administration of the trial medication). However, other factors may have contributed to the event (e.g., the participant's clinical condition, other concomitant events). Although an AE may rate only as "possibly related" soon after discovery, it can be flagged as requiring more information and later be upgraded to "probably related" or "definitely related", as appropriate.
- **Unlikely to be related** – A clinical event, including an abnormal laboratory test result, whose temporal relationship to study intervention administration makes a causal relationship improbable (e.g., the event did not occur within a reasonable time after administration of the study intervention) and in which other drugs or chemicals or underlying disease provides plausible explanations (e.g., the participant's clinical condition, other concomitant treatments).
- **Not Related** – The AE is completely independent of study intervention administration, and/or evidence exists that the event is definitely related to another etiology. There must be an alternative, definitive etiology documented by the clinician.

---

#### 8.3.3.3 EXPECTEDNESS

The PI and ISM will be responsible for determining whether an adverse event (AE) is expected or unexpected. An AE will be considered unexpected if the nature, severity, or frequency of the event is not consistent with the risk information previously described for the study intervention.

---

#### 8.3.4 TIME PERIOD AND FREQUENCY FOR EVENT ASSESSMENT AND FOLLOW-UP

The occurrence of an adverse event (AE) or serious adverse event (SAE) may come to the attention of study personnel during study visits and interviews of a study participant presenting for medical care, or upon review by a study monitor.

All AEs including local and systemic reactions not meeting the criteria for SAEs will be captured on the appropriate case report form (CRF). Information to be collected includes event description, time of onset, clinician's assessment of severity, relationship to study product (assessed only by those with the training and authority to make a diagnosis), and time of resolution/stabilization of the event. All AEs occurring while on study must be documented appropriately regardless of relationship. All AEs will be followed to adequate resolution.

Any medical condition that is present at the time that the participant is screened will be considered as baseline and not reported as an AE. However, if the study participant's condition deteriorates at any time during the study, it will be recorded as an AE.

Changes in the severity of an AE will be documented to allow an assessment of the duration of the event at each level of severity to be performed. AEs characterized as intermittent require documentation of onset and duration of each episode.

The PI and ISM will record all reportable events with start dates occurring any time after informed consent is obtained until 7 (for non-serious AEs) or 30 days (for SAEs) after the last day of study participation. At each study visit, the investigator will inquire about the occurrence of AE/SAEs since the last visit. Events will be followed for outcome information until resolution or stabilization.

---

#### 8.3.5 ADVERSE EVENT REPORTING

The PI ([name]) will comply with the NIMH Reportable Events policy. The intervention will continue for each subject so long as adverse events do not occur for that individual. The ISM will monitor data and review safety data. If adverse events related to the study (definitely related, probably related, or potentially related) do occur, they will be reported to the IRB within 7 days and will be reported to the PI immediately. All other adverse events will be reported annually at the time of IRB renewal.

---

#### 8.3.6 SERIOUS ADVERSE EVENT REPORTING

The study investigator shall complete an Unanticipated Adverse Device Effect Form and submit to the study sponsor and to the reviewing Institutional Review Board (IRB) as soon as possible, but in no event later than 10 working days after the investigator first learns of the effect. The study sponsor is responsible for conducting an evaluation of an unanticipated adverse device effect and shall report the results of such evaluation to the Food and Drug Administration (FDA) and to all reviewing IRBs and participating investigators within 10 working days after the

sponsor first receives notice of the effect. Thereafter, the sponsor shall submit such additional reports concerning the effect as FDA requests.

#### 8.3.7 REPORTING EVENTS TO PARTICIPANTS

N/A

#### 8.3.8 EVENTS OF SPECIAL INTEREST

N/A

#### 8.3.9 REPORTING OF PREGNANCY

N/A

### 8.4 UNANTICIPATED PROBLEMS

#### 8.4.1 DEFINITION OF UNANTICIPATED PROBLEMS (UP)

The Office for Human Research Protections (OHRP) considers unanticipated problems involving risks to participants or others to include, in general, any incident, experience, or outcome that meets all of the following criteria:

- Unexpected in terms of nature, severity, or frequency given (a) the research procedures that are described in the protocol-related documents, such as the Institutional Review Board (IRB)-approved research protocol and informed consent document; and (b) the characteristics of the participant population being studied;
- Related or possibly related to participation in the research (“possibly related” means there is a reasonable possibility that the incident, experience, or outcome may have been caused by the procedures involved in the research); and
- Suggests that the research places participants or others at a greater risk of harm (including physical, psychological, economic, or social harm) than was previously known or recognized.

This definition could include an unanticipated adverse device effect, any serious adverse effect on health or safety or any life-threatening problem or death caused by, or associated with, a device, if that effect, problem, or death was not previously identified in nature, severity, or degree of incidence in the investigational plan or application (including a supplementary plan or application), or any other unanticipated serious problem associated with a device that relates to the rights, safety, or welfare of subjects (21 CFR 812.3(s)).

#### 8.4.2 UNANTICIPATED PROBLEM REPORTING

The investigator will report unanticipated problems (UPs) to the reviewing Institutional Review Board (IRB) and to the Data Coordinating Center (DCC)/lead principal investigator (PI). The UP report will include the following information:

- Protocol identifying information: protocol title and number, PI's name, and the IRB project number;
- A detailed description of the event, incident, experience, or outcome;
- An explanation of the basis for determining that the event, incident, experience, or outcome represents an UP;
- A description of any changes to the protocol or other corrective actions that have been taken or are proposed in response to the UP.

To satisfy the requirement for prompt reporting, UPs will be reported using the following timeline:

- UPs that are serious adverse events (SAEs) will be reported to the IRB and to the DCC/study sponsor within 10 days of the investigator becoming aware of the event.
- Any other UP will be reported to the IRB and to the DCC/study sponsor within 10 days of the investigator becoming aware of the problem.
- All UPs should be reported to appropriate institutional officials (as required by an institution's written reporting procedures), the supporting agency head (or designee), and the Office for Human Research Protections (OHRP) within 10 days of the IRB's receipt of the report of the problem from the investigator.

---

#### 8.4.3 REPORTING UNANTICIPATED PROBLEMS TO PARTICIPANTS

N/A

## 9 STATISTICAL CONSIDERATIONS

### 9.1 STATISTICAL HYPOTHESES

The data will be collected throughout the course of the study by blinded test administrators. A General Linear/Logistic Mixed (GLLM) effects analytic model was developed in consultation with UM statistics department prior to our preliminary trial. GLLM is considered ideal when analyzing repeated measures as it treats time as a continuous variable and can account for missing data. This framework can readily adapt to subgroupings present in the data. GLLM analysis includes random and fixed effects. In this study, treatment order (active first vs sham first), treatment condition (active, active washout, sham, sham washout), baseline loudness, baseline TFI, and interaction of treatment and treatment order are treated as fixed while intercept is treated as a random effect. All metrics are computed relative to baseline for each subject.

MICHR has provided templates, tools, and general guidance in support of activities conducted by the study team to facilitate study and data management, and will continue to do so. The University of Michigan's Department of Statistics Consulting for Statistics, Computing and Analytics Research (CSCAR) has provided individualized support and training to our team on management, collection, and analysis of data for phase 1 (which is identical to the second except in terms of subject numbers and treatment duration). Staff are available for continued support in the use of technical software, and advanced computing in research.

- Primary Efficacy Endpoint(s):
  - 1) Objective Tinnitus Loudness
  - 2) Tinnitus Functional Index
  - 3) Tinnitus Handicap Index
- Secondary Efficacy Endpoint(s):
  - 1) Tinnitus bandwidth/spectrum
  - 2) Minimum masking level
  - 3) Tinnitus Hearing Survey

## 9.2 SAMPLE SIZE DETERMINATION

To compute statistical power, we utilized a linear model of our prior trial data, where change from baseline in both TFI and loudness is a linear function of the time in study, with a constant term reflecting enrollment in study. Time in study was extended out to six weeks. Data sample independence was achieved by normalizing each subject by their own baseline. With these parameters, alpha = 0.05 and beta = 0.8, we simulated new data sets with samples ranging from 5 to 50. Model slopes were tested for significant differences using analysis of covariance. Each new model was simulated 50 times, and the total number of significant models counted. The first sample size where the computed power was greater than 0.8 was determined. 14 subjects are required per arm to achieve a power of 0.8 for the loudness test, and 17 subjects are required per arm for the TFI. Thus, this study design requires a total subject count of 34. We propose a minimum sample size of 50 to account for subject variability and compliance.

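### The sample-size figures in Section 9.2 (14 and 17 per arm, 34 in total) do not describe this crossover or its planned model, Section 9.4.1 names no primary contrast, and the THI has no power figure

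*Combined protocol and SAP*

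**What the plan says.** Section 9.2 fits a linear model to Stage 1 data for change in TFI and loudness over time, then simulates from it. On duration it says "Time in study was extended out to six weeks". The test is described as follows: "Model slopes were tested for significant differences using analysis of covariance". On the number of runs it says "Each new model was simulated 50 times, and the total number of significant models counted". The rule for choosing the size reads "The first sample size where the computed power was greater than 0.8 was determined". The result, with loudness first and TFI second, is that "14 subjects are required per arm to achieve a power of 0.8 for the loudness test, and 17 subjects are required per arm". On the total, the section concludes "Thus, this study design requires a total subject count of 34", and on the size actually planned it adds "We propose a minimum sample size of 50 to account for subject variability and compliance". No slope, SD or within-subject correlation is given, and the THI is not mentioned.

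The rest of the plan describes something else:

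- **Design.** Sections 4.1 and 6.3 give a crossover in which every subject takes both active and sham, and only the order is randomised.
- **Model.** Sections 9.1 and 9.4.1 plan a mixed model for loudness, TFI and THI. Its fixed effects are order, a four-level condition, baseline loudness, baseline TFI and treatment by order, with a random intercept. The text says that time is handled as continuous, but no time or treatment-by-time term is listed.
- **Contrast.** Section 9.4.1 names none. The objectives table in Section 3 lists four time points for each endpoint (end of each arm and end of each washout) and ranks none of them.
- **Error rates.** Sections 9.2 and 9.4 both give beta as 0.8.

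**The concern.** A sample-size statement should say how likely the trial is to detect a stated effect with the test it will run. Section 9.2 differs from the plan on both counts. Doubling a per-arm number treats active and sham as separate groups of people, whereas here the same people supply both. The quantity tested is a slope difference, whereas the listed model estimates differences between conditions.

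This is the plan's only sample-size justification, and the goal of 50 subjects with complete data has no other stated basis. As long as the contrast is unnamed, slope, mean and end-of-arm comparisons all remain open for three primary endpoints, with final analysis after unblinding. Power cannot be computed for a test that has not been chosen.

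**Working it through.** **1. The plan's own figure.** 2 × 17 = 34, so the total reproduces. The 14 and 17 do not, because Section 9.2 gives no effect, SD or correlation.

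**2. Precision of 14 and 17.** With 50 runs the standard error at power 0.8 is √(0.8 × 0.2 / 50) = 0.057, or 5.7 points. The smallest count above 0.8 is 41 of 50, with exact 95% interval 0.69 to 0.91.

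For the stopping rule, assume that sizes run from 5 to 50 in steps of 1 (the step is not stated) and that true power at n per arm is Φ(2.8016·√(n/n80) − 1.96). Here n80 is the size with true power 0.8, and 2.8016 = 1.96 + 0.8416.

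- If n80 = 17, the rule picks 14 to 19 in 93% of repetitions, with mean true power 0.79 at the chosen size.
- Keeping the n80 values for which both tail probabilities of the reported size are at least 0.025, a reported 17 is compatible with n80 from 14.0 to 22.9, and a reported 14 with 11.2 to 18.7.
- With 2,000 runs the standard error is √(0.16/2000) = 0.009, and for n80 = 17 the 5th to 95th percentile of the chosen size narrows to 17 to 18.

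**3. What the crossover does to the TFI slope figure.** Two groups of n have slope-difference variance 2σ²/n. A crossover of N subjects with active-sham correlation 0 (assumed) has 2σ²/N. Power is therefore Φ(2.8016·k·√(N/n80) − 1.96), where k is the fitted slope difference as a fraction of the one assumed.

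**4. The extension to six weeks.** The Stage 1 abstract in the references reports 28 days of treatment. Suppose the effect grows linearly to week 4 and then stays level, at 1, 2, 3, 4, 4, 4.

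- Fitted over weeks 1 to 6, the slope is 11/17.5 = 0.629 of the assumed one.
- Fitted over weeks 0 to 6, it is 20/28 = 0.714.

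Slope power at N = 50:

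| n80 | linear to week 6 (k = 1) | held, weeks 1–6 (k = 0.629) | held, weeks 0–6 (k = 0.714) |
|---|---|---|---|
| 14 | >0.999 | 0.914 | 0.966 |
| 17 | 0.998 | 0.855 | 0.929 |
| 22.9 | 0.985 | 0.740 | 0.841 |

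**5. How much the contrast matters.** Assume equal variances, within-arm correlation r between weekly changes, active-sham correlation c, weeks 1 to 6 and a linear effect. The required N relative to a slope contrast is:

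- week-6 change: [(1 − c)/36] ÷ [(1 − r)/17.5]
- mean change over the arm: {[(1 + 5r)/6 − c]/3.5²} ÷ [(1 − r)/17.5]

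| r | c | week 6 / slope | mean / slope |
|---|---|---|---|
| 0.3 | 0 | 0.69 | 0.85 |
| 0.5 | 0 | 0.97 | 1.67 |
| 0.7 | 0 | 1.62 | 3.57 |
| 0.3 | 0.2 | 0.56 | 0.44 |
| 0.5 | 0.2 | 0.78 | 1.10 |
| 0.7 | 0.2 | 1.30 | 2.62 |

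The ratio runs from 0.56 to 1.62 for week 6 and from 0.44 to 3.57 for the mean.

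**6. THI.** Nothing can be computed, because the documents give no effect or SD.

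**The case against.** The strongest reply is that the mismatch does no harm. If 17 per group suffices for two separate groups, the same people measured under both treatments will normally need fewer. The summary of changes and Section 10.4 give the goal as 50 subjects with complete data, with up to 100 randomised, and Section 7.2 replaces treated subjects who withdraw. Even as a parallel comparison of 25 against 25, Φ(2.8016·√(25/n80) − 1.96) gives 0.83 to 0.96 across n80 from 22.9 down to 14. The step from 34 to 50 therefore absorbs most of the simulation error. Under the held effect at 50, power falls below 0.8 only with n80 near 22.9 and weeks 1 to 6. All of this stands, and it is why a reader who infers that the trial is underpowered goes further than the documents allow.

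It could also be said that the arms in Section 9.2 are the two sequences, 17 in each. The two-group reading is indeed an inference. But the protocol uses 'arm' for treatment or sham and 'group' for sequence, and on either reading a slope test is not the model in Section 9.4.1.

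A second tempting inference is that the simulation wrongly treated each subject's weekly scores as independent. Section 9.2 says only "Data sample independence was achieved by normalizing each subject by their own baseline". It does not mention weekly scores, and may mean independence between the active and sham samples. The point does not rely on it.

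The objectives table does suggest an end-of-arm comparison. It narrows the choice of contrast but does not settle it.

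**Conclusion.** The point holds as a mismatch between the justification and the plan. It should be fixed before unblinding. Four parts follow from the text alone: 14, 17 and 34 are not the requirement or power of this crossover under its planned model; no primary contrast is named; the THI has no figure; and beta of 0.8 should read power 0.8 (beta 0.2). The 50-run imprecision also follows, although the range of 14 to 23 around the reported 17 assumes steps of 1 and the normal power curve above.

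A power shortfall is not shown, and its direction cannot be settled from the documents. Ignoring the crossover probably overstates the number needed, while carrying a 28-day line to six weeks may understate it. The range of 0.74 to 0.97 at 50 subjects illustrates that second effect for a TFI slope contrast with active-sham correlation 0. It is not an estimate of this trial's power.

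**What to change.** 1. **Section 9.4.1:** name one primary active-versus-sham contrast, the same for each primary endpoint. The options are the end-of-arm (week 6) change, which is closest to the objectives table; the mean change over the arm; or a slope difference, with a treatment-by-time term added to the model.
2. **Section 9.2:** replace the calculation with a simulation of the 2×2 crossover under that model at two-sided 0.05. Use Stage 1 variances and within-subject correlations and at least 2,000 runs per size. Run it with the effect growing linearly to week 6 and with the effect held at its week-4 value.
3. Report power at 50 subjects with complete data for loudness, TFI and THI. If Stage 1 holds no THI data, state the effect and SD assumed.
4. Delete the per-arm wording and the doubled 34, and write power 0.8 (beta 0.2) in Sections 9.2 and 9.4.

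The cost is one sentence in Section 9.4.1, a few hours of simulation on data the team already used, and possibly a less favourable stated power. Enrolment and conduct do not change.

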## 9.3 POPULATIONS FOR ANALYSES

All subject's data will be analyzed in one cohort. We will perform both per-protocol and intention-to-treat analyses. While intention-to-treat analysis is ideal, our protocol may require subjects to adhere to a strict schedule in order to fully realize the benefit of the treatment. Our pilot study had excellent compliance rates, but a longer and larger study provides more opportunity for non-compliant subjects. Should sensitivity analysis between the intention-to-treat and per-protocol analyses attain significance, differences between compliant and non-compliant subjects will be further explored in an effort more fully understand who best can benefit from the bimodal protocol. Missing data and losses to follow-up will be managed using

a last observation carried forward approach. Sensitivity analysis to outliers will also be performed. If results differ significantly between with and without outliers, outliers will be further investigated to determine what factors impact the likelihood of a subject responding or being resistant to the treatment protocol.

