**NIH-FDA Phase 2 and 3 IND/IDE Clinical Trial Protocol Template**

	Expanding randomized subjects from 50 to up to 100	-some subjects that were enrolled during pandemic shutdown were not able to participate completely and have incomplete data, allows us to reach goal of 50 subjects with complete data
7.1, 8.2	Clarifying exclusion criteria	Clarifying exclusion criteria with TFI and TT
8.2	Adding online locations for consenting and medical screening, and 2 nd floor of Med Sci I for medical screening, and [name] for referrals as needed	Allows to meet online and prevent excessive in person appointments, allow [name] to refer as needed
8.2	Updating adverse event reporting to match IRBMED	Updating adverse event reporting timeline from 7 days to 14 days to match IRBMED

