### 1.3 SCHEDULE OF ACTIVITIES (SOA)

period		Arm 1		End Period 1	Washout	Arm 2		End Period 2	Washout	EOS	Post-study monitoring Weeks 28, 32, 36
visit	Screening	Baseline 1	End of weeks 1-5	End of week 6	End of week 7-11	End of week 12/Baseline 2	End of weeks 13-17	End of week 18	End of week 19-23	End of week 24	32, 36
day		Day 0	Days 7, 14, 21, 28, 35	Day 42	Days 49- 84	Day 91	Days 98, 105, 112, 119, 126	Day 133	Days 140- 168	175	252
window			'+ or - 3 days, but 5 days between weekly visits	'+ or - 3 days, but 5 days between weekly visits	'+ or - 3 days, but 5 days between weekly visits	'+ or - 3 days, but 5 days between weekly visits	'+ or - 3 days, but 5 days between weekly visits	'+ or - 3 days, but 5 days between weekly visits	'+ or - 3 days, but 5 days between weekly visits	'+ or - 3 days, but 5 days between weekly visits	'+ or - 3 days, but 5 days between weekly visits
	Informed Consent	x									
	Medical History	x									
	Tinnitus Maneuver Checklist	x		x	x			x		x	
	Audiogram	x	x	x	x	x	x	x	x	x	
	TFI	x	x	x	x	x	x	x	x	x	x
	THI	x	x	x	x	x	x	x	x	x	
	TinnTester	x	x	x	x	x	x	x	x	x	
	THS	x		x		x		x		x	
	MMI	x		x		x		x		x	

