### 7.3 LOST TO FOLLOW-UP

A participant will become ineligible to continue in the study if he/she misses more than one visit for each of the following 6-week time periods: Arm 1 treatment, Arm 1 washout, Arm 2 treatment, Arm 2 washout. It is not considered a protocol deviation if a subject misses only one visit in any 6-week time period. A participant will be considered lost to follow-up if he or she fails to return for 2 consecutive scheduled visits and is unable to be contacted by the study site staff.

The following actions must be taken if a participant fails to return to the clinic for a required study visit:

- The site will attempt to contact the participant and reschedule the missed visit within 1 week and counsel the participant on the importance of maintaining the assigned visit schedule and ascertain if the participant wishes to and/or should continue in the study.
- Before a participant is deemed lost to follow-up, the investigator or designee will make every effort to regain contact with the participant (where possible, 3 telephone calls, emails or portal messages).
- Should the participant continue to be unreachable, he or she will be considered to have withdrawn from the study with a primary reason of lost to follow-up. If participant refuses to return device, the Office of General Council and/or the UM Police department will be notified of device theft, pursuant to Mich. Comp. § 750.356(3), § 750.356a(1), "Felony Theft in Michigan".

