### 9.4.2 ANALYSIS OF THE SECONDARY ENDPOINT(S)

The following analytical framework will be applied to 2ndary measures (see section 3.2 for more details). Analyses are not dependent on primary-measures. All measures are ordinal, repeated measures. Data will be analyzed using repeated-measures ANOVA, and shown as mean+/-SEM. Normality will be assessed using Kolmogorov-Smirnoff tests, and non-parametric tests used for non-normally distributed data. To assess how the secondary measures might co vary with the primary measures, we will use principal component analysis or linear fixed effects models.

Non-compliant and missing data points will be excluded from analysis.

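### Section 9.3 carries the last observation forward with no arm boundary and is not reconciled with sections 9.1, 9.4.1 and 9.4.2; applied as written, it can bias the active-sham contrast and understate its standard error

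*Combined protocol and SAP*

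**What the plan says.** Section 9.3, after announcing both intention-to-treat and per-protocol analyses, states: "Missing data and losses to follow-up will be managed using" "a last observation carried forward approach". It names no endpoint, analysis set, visit or period, and does not say whether a value may pass from one arm or washout into the next.

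Sections 9.1 and 9.4.1 describe the primary model this way: "GLLM is considered ideal when analyzing repeated measures as it treats time as a continuous variable and can account for missing data". Neither mentions LOCF. The model has a random intercept and a four-level condition factor (each arm and its washout), so active and sham are compared within subject.

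Section 9.4.2, for the secondary endpoints, states: "Non-compliant and missing data points will be excluded from analysis".

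On the metric, section 9.1 says "All metrics are computed relative to baseline for each subject", while the schedule in section 1.3 has a visit labelled "End of week 12/Baseline 2". The plan does not say which baseline serves arm 2.

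Subjects with no arm-2 data are foreseeable. Section 7.3 makes a participant "ineligible to continue in the study if he/she misses more than one visit" in a six-week period, section 7.2 provides for withdrawal and replacement, and the summary of changes records that some subjects enrolled during the pandemic shutdown "were not able to participate completely and have incomplete data".

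**The concern.** In a parallel-group trial, LOCF fills a subject's gap with a value from the same treatment. Here every subject passes through both conditions. If a subject leaves before arm 2 and nothing stops the carrying, the arm-2 rows are filled with values recorded in arm 1 or its washout but labelled with the other condition.

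Two consequences follow. The active-sham contrast is diluted, usually toward zero. The model also counts the filled rows as real measurements, so its standard error can be too small.

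Section 9.4.1 places the final analysis after unblinding. An unsettled missing-data rule would then be settled by people who can see the treatment codes.

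**Working it through.** **1. The plan's own figures.** The plan gives no dropout rate, effect size or SD. Section 9.2's total follows from 17 × 2 = 34, but the 14 and 17 per arm cannot be reproduced because the slopes and variances from the prior trial are not shown. The sizes below are therefore illustrations.

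**2. Inputs.**

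| Input | Value | Source |
|---|---|---|
| Blocks | 4 blocks of 6 weekly visits | sections 1.3, 6.1.2 |
| Subjects | 50, i.e. 25 per order | minimum in 9.2; 1:1 in 6.3 |
| Model | random intercept; order, condition, their interaction, baseline TFI | 9.4.1 |
| Week-6 active-sham TFI difference | −13 | assumed; 13 points is the change called clinically significant in 3.1 |
| Between- and within-subject SD | 10 and 8 | assumed |
| Weekly residuals | independent | assumed |
| Sham response | none | assumed (except step 6) |
| Loss p | 10% or 25%, at random | assumed |

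The effect builds linearly to week 6 and fades linearly to zero over washout. Change is from the original baseline. Baseline loudness was not simulated, and no separate time term was fitted because section 9.4.1 lists none among the fixed effects.

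**3. Complete-data value.** The model averages over weeks 1 to 6: −13 × (1+2+3+4+5+6)/36 = −7.58, or about −7.6.

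**4. Mechanism by hand.** Let a fraction p of each order be lost at the end of arm 1.
- End-of-arm contrast: the active mean is −13(1−p/2) and the sham mean is −13(p/2), so the contrast is −13(1−p), which gives −11.7 at 10% and −9.75 at 25%.
- If change is taken from Baseline 2, or the carried value is a washout value that has returned to baseline, the contrast is −13(1−p/2), which gives −12.35 and −11.375.
- On the model scale, the active-first contrast is −7.58 + 13p and the sham-first contrast is −7.58(1−p). Their mean is −7.58 + p(13+7.58)/2, which gives −6.55 and −5.01. Simulation gave −6.6 and −5.0.

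**5. Simulation, loss spread over 24 weeks (2,000 runs per scenario).**

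| | 10% loss | 25% loss |
|---|---|---|
| LOCF, no boundary: contrast | −7.2 | −6.5 |
| Model SE / actual SD | 0.68 / 0.73 | 0.66 / 0.80 |
| 95% CI coverage, LOCF | 89% | 60% |
| 95% CI coverage, observed visits | 96% | 97% |

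Observed visits gave contrasts of −7.5 to −7.6. LOCF stopped at each block gave −7.4 to −7.6 with coverage of 92–96%.

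The fall in coverage has two sources. The SE ratios are 0.68/0.73 = 0.93 and 0.66/0.80 = 0.825. With no bias, coverage would be 2Φ(1.96 × ratio) − 1, or about 93% and 89%. Adding the bias (0.4/0.73 = 0.55 and 1.1/0.80 = 1.4 actual SDs) brings it to about 89% and 60%. At 25% loss, most of the fall is therefore bias toward zero.

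A different assumed time course, with a complete-data contrast of −13, shows the same pattern. At 10%, 20% and 30% loss, unbounded LOCF gave −12.5, −12.0 and −11.5, SE ratios of 0.85, 0.77 and 0.71, and coverage of 85%, 64% and 39%.

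**6. No true difference** (both arms assumed to reach −10, spread loss). False positives under unbounded LOCF were 5.3% at 10% loss and 8.7% at 25%. Analyses of observed visits stayed between 3.5% and 4.9%.

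**7. Limits.** With loss only in the active period (7%), the SE ratio under LOCF was 0.99, so the understatement is not universal. With lag-1 residual correlation of 0.5, the random-intercept model on observed visits, without any LOCF, had an SE ratio of about 0.65 and coverage of about 80%.

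**The case against.** The strongest reply is that section 9.3 never orders carrying across arms. Any careful analyst would stop at the end of each block, and then the bias is small. That stands as far as it goes. A reader might infer that the plan requires cross-arm carrying, and the text does not support that. It does not rule it out either, and one clause would have done so.

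A reader might also count three contradictory missing-data rules. Only sections 9.3 and 9.4.2 conflict directly. Sections 9.1 and 9.4.1 describe a property of the model, which leaves the primary analysis unreconciled with LOCF but does not contradict it.

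LOCF may be defended as conservative. For the bias this is largely right under random loss with a real benefit. It does not cover the standard error: with no true difference the contrast is unbiased, yet false positives still rise at the higher loss rate.

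A reader might go further and infer that LOCF would exaggerate the benefit, through a sham response with unequal loss or through subjects stopped for worsening on active. Both are possible arithmetically, but the documents do not support expecting them. The strong placebo effect in section 4.2 concerns earlier studies of other tinnitus treatments, and the same section says this placebo stimulus had no effect in the first trial. The discontinuation criterion in section 7.1 needs a TFI rise of at least 16 and an average 12 dB loudness rise on two consecutive weekly measures, and section 8.2 would stop the study if 10% persistently worsened.

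The per-protocol analysis, the replacement of withdrawn subjects and the expansion to 100 soften the practical effect. They do not say what happens to incomplete subjects in the intention-to-treat analysis.

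**Conclusion.** The concern holds in conditional form. Section 9.3 conflicts directly with section 9.4.2, is not reconciled with sections 9.1 and 9.4.1, and sets no arm boundary. If it is applied without one, the active-sham contrast usually shrinks toward zero and its standard error can be too small.

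On the stated assumptions the attenuation is about 0.4 points at 10% spread loss and 1.1 points at 25%, out of 7.6. False positives are near nominal at 10% loss and about 8–9% at 25%. The mechanism follows from the design; its size depends wholly on assumed effect, SDs, residual independence, and the amount and timing of loss. The point should be fixed before unblinding. It does not show that the trial's result would be wrong.

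**What to change.** In section 9.3, state that the primary intention-to-treat analysis fits the section 9.4.1 mixed model to all observed visits of every randomised subject, including those later replaced under section 7.2, without imputation and assuming data are missing at random. Delete LOCF, or keep it only as a labelled sensitivity analysis in which no value crosses a six-week block boundary.

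In section 9.4.2, state that the same no-imputation rule governs missing secondary data. To keep a subject's other visits, use the same mixed model there in place of repeated-measures ANOVA, which conventionally drops incomplete subjects. A delta-adjusted sensitivity analysis for departures from missing at random is optional.

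The cost is revised wording, a change of method for the secondary endpoints and slightly more analysis work. Visits and participation are unaffected. Reported standard errors will be wider than under LOCF, and the primary result will rest on missing at random. The change does not cure any standard-error understatement that serially correlated weekly residuals cause in a random-intercept-only model.
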